7.1.1 Determination of Sample Size

The primary efficacy analysis will be based on the calculation of the observed overall response rate (ORR) and its posterior probability distribution. An observed ORR of 60% is considered to be clinically important while a true ORR of 45% or less is considered to be too low to merit adoption of ITD combination therapy.

Evidence of efficacy of ITD combination therapy might be reasonably concluded if the observed ORR is $\geq 60\%$ (i.e. a clinically important result is observed) and there is $\geq 90\%$ posterior probability that the true ORR is $> 45\%$ (i.e. a sufficiently high level of proof that the true ORR is not lower than the historical rate (internal review)).

The justification of the sample size is accordingly based on this Bayesian approach to “proof of concept” (PoC) in phase II trials ((21)).

A minimally informative prior distribution for the true ORR with a median equal to the clinical threshold for futility (45%) will be used, namely the Beta distribution (Beta(a, b)) where $a = \ln(0.5) / \ln(0.45) = 0.86805$ and $b = 1$. This prior distribution is equivalent to assuming we have prior information on approximately 1.87 patients. The posterior probability for an ORR $> 45\%$ given “x” overall responses out of “n” patients is given by the right tail (from $p = 0.45$ to $p = 1.0$) of the Beta(a+x, b + n - x) distribution.

For $n = 45$ and a true ORR of 65%, the probability of declaring efficacy, based on this approach, is 0.80. Accordingly, provision is being made to register 45 patients on the trial. When we observe a rate of 60% or more (i.e. when the first PoC criterion is met) the posterior probability, that the true ORR is $> 45\%$, is 90% when the observed rate is based on at least 20 patients (in which case the second PoC criterion is

automatically met) and 95% when the observed rate is based on at least 31 patients. Consequently, if accrual is slow and the trial is terminated early for this reason, there is still scope to demonstrate PoC.

7.1.2 Randomization and Stratification -Not applicable

7.1.3 Populations for Analysis

Data from all patients registered on the study, the FAS, will be collected and, following the intention to treat principle, the analysis of efficacy will be based on the FAS. Analysis of safety and tolerability will be based on the Safety Set – the subset of patients in the FAS who received at least one dose of ixazomib.

7.1.4 Procedures for Handling Missing, Unused, and Spurious Data

Patients without re-staging information for any reason and who are not known to have achieved at least a PR while on ITD therapy will be deemed to have not met the primary efficacy endpoint. Time to event data will be censored at the study censor date (see below) except for patients deemed lost to follow-up – their time to event data will be censored at the earlier of the study censor date and the date of last assessment. Missing quality of life data will, in linear mixed model analyses, be assumed to be missing at random, but if the missingness is due to death or withdrawal from the study due to unacceptable toxicity or progression, the missing measures will be imputed and the patient deemed to have “zero” global quality of life from the date of withdrawal from the study.

7.1.5 Demographic and Baseline Characteristics

Demographic and baseline characteristics such as gender, age, race, weight, height, BSA, primary diagnosis, and other parameters will be summarized descriptively for the FAS. Categorical data will be presented as frequencies and percentages. For continuous data, means, standard deviations, medians, 25th and 75th percentiles, minima and maxima will be presented.

7.1.6 Efficacy Analysis

The primary efficacy objective is to determine the overall response rate to treatment with ITD combination therapy in RRMM patients. Overall response is defined as achievement of a PR or better

(PR, VGPR, CR or sCR) as defined by the IMWG criteria (Appendix 4). The overall response rate (ORR) will be calculated as the number of patients who have experienced at least a partial response, divided by the number of patients registered on the trial. Patients who withdraw from the study prior to re-staging, or who are lost to follow-up before re-staging and are not known to have achieved at least a PR, or whose re-staging information is missing for any reason, will be considered to have not met the primary efficacy endpoint.

The primary efficacy analysis will be based on the calculation of the observed ORR and its posterior probability distribution. Evidence of efficacy of the ITD combination therapy will be based on two PoC criteria:

1. Observed ORR \geq 60%
2. Posterior probability that the true ORR exceeds 45% is $>$ 90% (given the observed data)

In addition, the percentiles of the posterior probability distribution for ORR, in particular the 95% uncertainty interval, defined by the 2.5 and 97.5 percentiles and also the posterior probability that the true ORR exceeds 45%, will be reported. The analysis will use a minimally informative prior distribution for the ORR, namely, Beta($a=0.86805$, $b=1$) for which the median ORR is 45% and the amount of prior information is equivalent to approximately 1.87 ($=a+b$) patients.

If an interim analysis of ORR is required for any reason (e.g. a review of efficacy by the TMC or sponsor), the posterior probability distribution will be updated, using the minimally informative prior distribution and the accumulated data, and reported as appropriate.

the study censor date for PFS is the earliest of the last dates of disease response assessment of those patients who remain on study (i.e. those patients who have not withdrawn or have not been deemed to be lost-to-follow-up). Patients who have withdrawn or have been lost to follow-up before the censor date will have their PFS censored at the date of their last disease response assessment on study. For each of these time-to-event endpoints (DOR and PFS), Kaplan-Meier (product-limit) estimates of duration times will be reported together with conventional 95% confidence intervals for the median duration time (using the Brookmeyer and Crowley method) and the survival function (using Greenwood's formula and the complementary log-log transformation). For patients with a BMAT at the time of the serological CR assessment, a landmark analysis of PFS will be conducted using a Cox proportional hazards regression model to investigate the association of PFS with the level of MRD.

The repeated assessment of quality of life will be analysed by fitting a linear mixed model. Details of these analyses of the secondary endpoints will be documented in the Statistical Analysis Plan (SAP) prior to locking the database for the primary efficacy analysis.

7.1.7 Safety Analysis

The co-primary objective of the trial is to evaluate the safety and tolerability of ITD combination therapy. These evaluations will be conducted on the Safety Set. Treatment emergent adverse events, i.e. newly occurring or worsening AE's that occur after the first dose of study drug, will be defined as per the CTCAE v4.03 and will be summarised by system organ class and/or preferred term as counts and percentages of participants with further subdivision based on severity and relationship to ITD therapy. Particular attention will be given to (i) rates of peripheral neuropathy (either sensory and/or painful) and cardiac toxicities \geq Grade 2, (ii) cessation of ixazomib and/or thalidomide and/or dexamethasone due to unacceptable toxicity, and (iii) subject withdrawal due to unacceptable toxicity. Total dose and percentage of planned dose (PPD) will be summarized, by cycle, for each of ixazomib, thalidomide and dexamethasone and will also be summarized for the accumulated first 4 cycles of ITD therapy. PPD is the total dose delivered divided by the per-protocol planned total dose, expressed as a percentage. The summaries of total dose and PPD will consist of means, standard deviations, medians, 25th and 75th percentiles, minima and maxima. Listings of worst grades of toxicities, by patient and cycle and up to 30 days after the last dose of study drug, will be generated as an Appendix to the report

of the primary analysis and, as required, for the TMC or sponsor.

Adverse events will be tabulated according to the NCI CTCAE version 4(19), as a guideline, whenever possible will include the following categories:

Treatment-emergent AEs

- ☐ Drug-related treatment-emergent AEs
- ☐ Grade 3 or higher treatment-emergent AEs
- ☐ Grade 3 or higher drug-related treatment-emergent AEs
- ☐ The most commonly reported treatment-emergent AEs (ie, those events reported by 10% of all patients)
- ☐ Serious adverse events

A listing of treatment-emergent AEs resulting in study drug discontinuation will be provided.

All patients who commence the combination therapy are in the “safety set” and will be included in these safety summaries until 30 days after they permanently cease one or more of the components of the combination. Thereafter, for patients remaining on just one or two of the agents, safety data will be reported in the form of listings. Newly emerging or worsening AE’s that occur in the 30-day period after a patient permanently ceases one or more agents in the combination therapy will be included in both the tabular summaries for combination therapy and in the listings for single or double agent therapy.

If appropriate, additional safety summaries will be reported in order to more clearly enumerate rates of toxicities and to further define the safety profile of ixazomib.

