3. STUDY ENDPOINTS

3.1 Primary Endpoints

The primary efficacy endpoint is the achievement of an overall response (sCR + CR + VGPR + PR + MR) as defined by International Myeloma Working Group (IMWG) criteria while on ITD combination therapy.

The co-primary safety endpoints are the incidence and severity of adverse events while on ITD therapy and the tolerability endpoints are total dose and percentage of planned dose of each study drug delivered in each cycle.

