4. STUDY DESIGN

4.1 Overview of Study Design

Single arm, multi-centre phase 2 trial of the combination of ixazomib with a thalidomide/dexamethasone backbone.

Treatment is with ixazomib 4mg on day 1, 8, 15 plus thalidomide 100mg daily and dexamethasone 40mg once weekly until disease progression, unacceptable toxicity or withdrawal of patient consent, whichever occurs first.

Drug	Dose	Schedule (1 cycle = 28 days)
Ixazomib	4mg	Days 1, 8 and 15 of 28 day cycle
Thalidomide	100mg	Days 1-28 of 28 day cycle
Dexamethasone	40mg	Days 1, 8, 15, 22 of 28 day cycle

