6.3 Dose-Modification Guidelines

Causality of adverse events will be assigned by the treating clinician at the time of occurrence and dose-modifications undertaken accordingly. Where there is an overlap of toxicity profile, dose reduction of offending agent as determined by the treating clinician will be undertaken. For example; myelosuppression (haematological AE) would result in dose reduction of ixazomib in the first instance, whereas peripheral neuropathy would result in dose reduction of thalidomide initially.

6.3.1 Recommended Ixazomib, Thalidomide and Dexamethasone Criteria for Beginning or Delaying a Subsequent Treatment Cycle & Dose Modifications for Treatment Associated Toxicity

Treatment with the combination of ixazomib/thalidomide/dexamethasone will use a cycle length of 28 days. For a new cycle of treatment to begin, the patient must meet the following criteria:

- ANC must be $\geq 1,000/\text{mm}^3$.
- Platelet count must be $\geq 75,000/\text{mm}^3$.
- All treatment-related non-hematologic toxicity (except for alopecia) must have resolved to \leq Grade 1 or to the patient's baseline condition except for isolated gamma glutamyl transferase (GGT) elevations.

If the patient fails to meet the above-cited criteria for initiation of the next cycle of treatment, dosing should be delayed for 1 week. At the end of that time, the patient should be re-evaluated to determine whether the criteria have been met. If the patient continues to fail to meet the above-cited criteria, delay therapy and continue to re-evaluate. The maximum delay before treatment should be discontinued will be 3 weeks or at the discretion of the Principal Investigator.

For dosing recommendations upon recovery, refer to Table 6-2 and Table 6-3.

Table 6-1 Ixazomib Dose Adjustments

Dose Level	Dose (mg)
Starting Dose	4.0 mg
-1	3.0 mg
-2	2.3 mg
-3	Discontinue

Note: If ixazomib is discontinued patients may continue thalidomide and dexamethasone and therefore remain on study.

Dosage adjustments for hematologic toxicity are outlined in Table 6-2.

Table 6-2 **Ixazomib and Thalidomide** Dose Adjustments for Hematologic Toxicities

Criteria	Action
Within-Cycle Dose Modifications	

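### The co-primary tolerability measures, total dose and percentage of planned dose, do not register delays between cycles: a 1- or 2-week delay with full dosing still scores 100%.

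*Protocol*

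**What the plan says.** Section 3.1 of the Protocol makes tolerability part of the co-primary safety endpoint: "the tolerability endpoints are total dose and percentage of planned dose of each study drug delivered in each cycle". Section 7.1.7 gives the formula, "PPD is the total dose delivered divided by the per-protocol planned total dose, expressed as a percentage", and adds that total dose and PPD "will also be summarized for the accumulated first 4 cycles of ITD therapy". Both windows are counted in cycles, not in calendar time.

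Section 6.3.1 sets the rule for starting a cycle. "Treatment with the combination of ixazomib/thalidomide/dexamethasone will use a cycle length of 28 days", and recovery criteria for neutrophils, platelets and non-haematologic toxicity must be met before the next one begins. "If the patient fails to meet the above-cited criteria for initiation of the next cycle of treatment, dosing should be delayed for 1 week". The patient is then re-evaluated and can be delayed again: "The maximum delay before treatment should be discontinued will be 3 weeks or at the discretion of the Principal Investigator".

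Table 6-2 adds that a restart delayed by more than 2 weeks leads to a dose-level reduction. The wording is partly conditional: the thalidomide step applies if ixazomib was already reduced in the preceding cycle. The same table has doses withheld within a cycle when counts fall below its limits.

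**The concern.** Postponing the cycle is the Protocol's first response when toxicity has not resolved by its planned start. All three drugs wait. Once the cycle begins and every dose is taken, total dose for the cycle is full and PPD is 100%, exactly as for a patient who had no toxicity. The 4-cycle summary has the same property, because it adds up cycles rather than weeks.

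Section 7.1.7 names summaries of adverse events, drug cessation and withdrawal for toxicity. It names none of cycle delays, actual cycle length or dose intensity. The trial could therefore report that nearly all planned dose was delivered for a regimen given at a clearly lower weekly rate than intended.

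The trigger is plausible. Table 1-3 reports thrombocytopenia in 28%, neutropenia in 25% and peripheral neuropathy in 26% of 173 patients on oral ixazomib combinations. The platelet limit for entry (75,000/mm³) is also the limit for starting a cycle. The Protocol does not say how often delays are expected.

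**Working it through.** The Protocol states no expected PPD, so there is no figure of its own to reproduce. The check applies its definition to delayed courses and compares the result with a time-adjusted measure.

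**Inputs**
- Planned dose per 28-day cycle (Section 4.1): ixazomib 4 mg on "Days 1, 8 and 15 of 28 day cycle", so 3 × 4 = 12 mg; thalidomide 100 mg on "Days 1-28 of 28 day cycle", so 28 × 100 = 2800 mg; dexamethasone 40 mg on 4 days, so 160 mg.
- Delay of d weeks before a restart (Section 6.3.1): d = 1, 2 or 3.

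**Formulas**
- PPD = mg delivered / mg planned.
- Relative dose intensity (RDI) = (mg delivered / elapsed weeks) / (planned mg per week). For the same set of cycles this equals PPD × planned days / elapsed days.

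**Full doses taken, delays of up to 2 weeks.** PPD is 100% for all three drugs in every case below.
- One cycle plus its delay, RDI = 28/(28 + 7d): 28/35 = 80.0% for 1 week; 28/42 = 66.7% for 2 weeks.
- Four cycles with cycles 2, 3 and 4 all delayed, RDI = 112/(112 + 21d): 112/133 = 84.2% for 1 week each; 112/154 = 72.7% for 2 weeks each.
- Four cycles with only one restart delayed, RDI = 112/(112 + 7d): 112/119 = 94.1% for 1 week; 112/126 = 88.9% for 2 weeks.

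**Delays of 3 weeks.** With no dose reduction the same formulas give 28/49 = 57.1% for one cycle and 112/175 = 64.0% over four. These figures set aside the reduction in Table 6-2, so they are not the general case. As an illustration, assume three 3-week delays with reductions alternating between ixazomib and thalidomide, ixazomib first, at the levels in Tables 6-1 and 6-4:
- Ixazomib 12 + 9 + 9 + 6.9 = 36.9 of 48 mg: PPD 76.9%; RDI 76.9% × 112/175 = 49.2%.
- Thalidomide 2800 + 2800 + 1400 + 1400 = 8400 of 11,200 mg: PPD 75.0%; RDI 48.0%.
- Dexamethasone 640 of 640 mg: PPD 100%; RDI 64.0%.

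Here PPD falls for the two reduced drugs, so the long delay is partly visible, but the lost time is not. The PPD figures use the starting dose as denominator. If planned dose were taken to mean the reduced dose, PPD would again be 100%.

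**Holds within a cycle.** One withheld ixazomib dose gives 8/12 = 66.7%. Seven withheld thalidomide days give 21/28 = 75%. PPD captures these.

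**The case against.** The strongest reply is that PPD is clearly defined and purely descriptive. No threshold, test or decision depends on it: the efficacy claim rests on the response rate, and the early-stopping rule on grade 3 or higher non-haematological toxicity. The toxicity behind a delay is reported elsewhere. Adverse event incidence and severity are co-primary, worst grades are listed by patient and cycle, and under Section 8.1.1 a laboratory value that delays treatment can count as an adverse event. Section 7.1.7 also allows further safety summaries, and exposure tables are often left to the SAP.

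Most of this stands, and it limits the consequence. It does not close the gap. The endpoint itself is fixed in Sections 3.1 and 7.1.7, Section 7.1.6 defers to the SAP only the detail of the secondary-endpoint analyses, and none of the listed adverse event categories identifies events leading to delay.

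Three stronger readings are tempting, and the Protocol does not support them.
- A reader might infer that PPD stays at 100% however long the delay. Table 6-2 attaches a dose reduction to delays beyond 2 weeks, and 3 weeks is the general maximum.
- A reader might infer that the per-cycle tables include only patients who started that cycle, so that early stoppers flatter the later cycles. Section 7.1.7 says the evaluations use the Safety Set and states no such denominator. Its rule on when patients leave the safety summaries is not tied explicitly to the dose tables.
- A reader might infer that protocol dose reductions will count as 100%. Section 4.1 gives one planned dose per drug, so the starting dose is the natural reading. A one-line statement would settle it.

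**Conclusion.** The point holds in a limited form. Total dose per cycle and PPD do not register delays between cycles. For a delay of 1 or 2 weeks with full dosing, PPD is 100% at a dose intensity of 80% or 67% for that cycle. Over 4 cycles the intensity is 84% or 73% if cycles 2, 3 and 4 are all delayed, and 94% or 89% if only one is. Delays beyond 2 weeks are partly captured through the conditional reduction in Table 6-2, and doses withheld within a cycle are captured.

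The figures assume that every dose is taken once the cycle starts. The effect on the reported summary depends on how often delays occur, which the Protocol does not give. Because the measure is descriptive, no formal conclusion of the trial changes. What is affected is how a co-primary tolerability result can be read, and that justifies the change.

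**What to change.** In Sections 3.1 and 7.1.7:
- Add RDI for each drug over the first 4 cycles: milligrams delivered per elapsed week, from cycle 1 day 1 to the end of the last cycle started, divided by planned milligrams per week at the Section 4.1 starting dose (3 mg ixazomib, 700 mg thalidomide, 40 mg dexamethasone).
- Report the number and length of cycle delays.
- Report the percentage of the Safety Set starting each of cycles 2, 3 and 4, with the reason for not starting (toxicity, progression, other). This also covers patients who are delayed and never restart, whom RDI would miss.
- State that the PPD denominator is the Section 4.1 starting dose.

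Do not enter zero dose after discontinuation for progression or withdrawal of consent. Section 4.3 expects an average of only 4 cycles per patient, so zero-filling would record loss of disease control as poor tolerability.

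The cost is a few table rows and probably a slightly less favourable tolerability figure. The inputs are the doses that PPD already needs and the Day 1 dates of cycles, which are scheduled visits. No dosing or delay rule changes.

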Grade 4 nonhematologic toxicities judged to be related to ixazomib and/or thalidomide	
 • Consider permanently discontinuing ixazomib and/or thalidomide 	Exceptions are cases in which the investigator determines the patient is obtaining a clinical benefit

Once any study drug/s is/are reduced for any toxicity, the dose may not be re-escalated. If any of ixazomib, thalidomide or dexamethasone is discontinued permanently patients may remain on study with the remaining agent/s.

For other side effects (ie constipation) symptomatic management (aperients etc.) should be attempted prior to a dose reduction.

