8.2 Procedures for Reporting Serious Adverse Events

AEs may be spontaneously reported by the patient and/or in response to an open question from study personnel or revealed by observation, physical examination, or other diagnostic procedures. Any clinically relevant deterioration in laboratory assessments or other clinical finding is considered an AE. When possible, signs and symptoms indicating a common underlying pathology should be noted as one comprehensive event. For serious AEs, the investigator must determine both the intensity of the event and the relationship of the event to study drug administration.

AEs which are serious must be reported to Millennium Pharmacovigilance (or designee) from the first dose of study drug through 30 days after administration of the last dose of ixazomib. Any SAE that occurs at any time after completion of ixazomib treatment or after the designated follow-up period that the sponsor-investigator and/or sub-investigator considers to be related to any study drug must be reported to Millennium Pharmacovigilance (or designee). In addition, new primary malignancies that occur during the follow-up periods must be reported, regardless of causality to study regimen, for a minimum of three years after the last dose of the investigational product, starting from the first dose of study drug. All new cases of primary malignancy must be reported to Millennium Pharmacovigilance (or designee).

Planned hospital admissions or surgical procedures for an illness or disease that existed before the patient was enrolled in the trial are not to be considered AEs unless the condition deteriorated in an unexpected manner during the trial (e.g., surgery was performed earlier or later than planned). All SAEs should be monitored until they are resolved or are clearly determined to be due to a patient's stable or chronic condition or intercurrent illness(es).

Since this is an investigator-initiated study, the principal investigator [name], also referred to as the sponsor-investigator, is responsible for reporting serious adverse events (SAEs) to any regulatory agency and to the sponsor- investigator's EC or IRB.

Regardless of expectedness or causality, all SAEs must also be reported in English to Millennium Pharmacovigilance (or designee):

Fatal and Life Threatening SAEs within 24 hours of the sponsor-investigator's observation or awareness of the event

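### The safety tables stop counting a patient's adverse events 30 days after any one drug is dropped, so they understate incidence over the whole course of study treatment

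*Protocol*

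**What the plan says.** Section 7.1.7 evaluates safety on the Safety Set, with treatment-emergent events "summarised by system organ class and/or preferred term as counts and percentages of participants". It then limits how long each patient contributes. Patients are "included in these safety summaries until 30 days after they permanently cease one or more of the components" of the combination. After that, "for patients remaining on just one or two of the agents, safety data will be reported in the form of listings". Events in the 30-day overlap go into both the tables and the listings. The section also allows that, if appropriate, "additional safety summaries will be reported in order to more clearly enumerate rates of toxicities".

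Dropping a component does not end study treatment. Section 6.3.1 says: "If any of ixazomib, thalidomide or dexamethasone is discontinued permanently patients may remain on study with the remaining agent/s". The note under Table 6-1 says the same for ixazomib, and section 6.3.2 for dexamethasone.

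Section 7.1.7 uses a longer window elsewhere: its worst-grade toxicity listings, by patient and cycle, run to 30 days after the last dose of study drug.

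Section 3.1 makes incidence and severity of adverse events a co-primary endpoint, assessed during ITD therapy. It ties the response endpoint to the period on ITD combination therapy in the same way. Section 7.1.6 calculates the response rate as the "number of patients who have experienced at least a partial response, divided by the number of patients registered on the trial" and does not repeat that window.

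**The concern.** The tables are crude percentages, and no adjustment for exposure is stated. A patient who stops one agent remains in the denominator while later events leave the numerator, even though the patient may still be taking one or two study drugs.

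Two consequences follow.

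- **The cut-off is related to the outcome.** Agents are often stopped for toxicity, so the patients most prone to it may be tabulated for the shortest time.
- **Events on the investigational drug can be left out.** A patient who stops dexamethasone and continues ixazomib with thalidomide leaves the tables 30 days after the steroid ends. A patient who stops thalidomide for neuropathy and continues ixazomib leaves in the same way, so neuropathy that worsens later is not tabulated. Section 7.1.7 singles out neuropathy for particular attention.

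A listing preserves these events but yields no incidence, and incidence is the endpoint.

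**Working it through.** **Figures stated in the plan.** None depends on this rule. The neighbouring design figures reproduce: at least 27 responders of 45 gives power 0.806 at a true rate of 65% (stated 0.80). The safety monitoring rule gives 0.049 and 0.804 at n = 12, and 0.051 and 0.801 at n = 36 (stated 0.05 and 0.80). The issue is the choice of window, not an arithmetic error.

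**Direction.** The tabulation window ends at the earlier of first component drop and end of all treatment, plus 30 days. The whole-course window ends at the end of all treatment, plus 30 days. The first lies inside the second and the denominator is the same, so the tabulated percentage can only be equal or lower.

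**Size: inputs.**

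- Average treatment: 4 cycles (section 4.3) of 28 days = 112 days, about 3.68 months. Stop-all hazard s = 1/3.68 = 0.272 per month.
- First event of interest: h = 0.08 per month (assumed).
- Dropping a component: c = 0.05, 0.10 or 0.15 per month (assumed; the protocol gives no rate).
- The 30-day tail is taken as 1 month. Times are exponential and independent, and h is unchanged after a drug is dropped.

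**Formula.** If follow-up ends at T + 1 month and T is exponential with hazard m, then P(event counted) = 1 − e^(−h) × m/(m + h), with e^(−0.08) = 0.9231.

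| Window | m | Calculation | Incidence | Gap |
|---|---|---|---|---|
| 30 days after last dose of any study drug | 0.272 | 1 − 0.9231 × 0.272/0.352 | 28.7% | – |
| Protocol tables, c = 0.05 | 0.322 | 1 − 0.9231 × 0.322/0.402 | 26.1% | 2.6 points |
| Protocol tables, c = 0.10 | 0.372 | 1 − 0.9231 × 0.372/0.452 | 24.0% | 4.7 points |
| Protocol tables, c = 0.15 | 0.422 | 1 − 0.9231 × 0.422/0.502 | 22.4% | 6.3 points |

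For 45 patients this is 45 × 0.026 = 1.2 to 45 × 0.063 = 2.8 patients missing from a row of the table.

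**Sensitivity to treatment length.** A separate simulation fixed the treatment length and set the whole-course incidence at 30% or 50%. It assumed that 10, 20 or 40% drop a component by the end of cycle 4, with the same drop hazard continuing afterwards.

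| Treatment length | Whole-course 30% is tabulated as | Whole-course 50% is tabulated as |
|---|---|---|
| 4 cycles | 28.9 / 27.8 / 25.3% | 48.3 / 46.7 / 42.8% |
| 12 cycles | 26.3 / 23.0 / 17.2% | 44.3 / 39.1 / 30.0% |

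The gap is about 1 to 7 points at 4 cycles and about 4 to 20 points at 12 cycles.

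**The case against.** The strongest defence is that the rule answers the question the protocol asks. The co-primary objective is the safety of the combination, and section 7.1.7 openly separates combination tables from one- and two-agent listings. That is a prespecified on-combination analysis. Later events are listed, worst grades are listed to 30 days after the last dose, and further summaries are allowed. All of this stands, and it is why the combination-only table should remain. It does not supply a rate for the treatment course that the protocol permits, because the further summaries are discretionary.

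A second objection concerns the model. It treats events and drops as independent. If a grade 3 event itself causes the drop, that patient is already counted in an overall grade 3 or higher row and cannot be lost from it. The loss then falls on other event terms and on later worsening. The model also leaves the hazard unchanged after a drug is removed. Both points stand, so the figures are illustrations and not estimates.

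Two stronger readings are tempting but not supported.

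- **That responses count without limit while harms are cut off, so benefit is favoured over harm.** Section 3.1 limits response to the period on ITD combination therapy, and section 7.1.4 uses a similar limit for patients without re-staging data. The two endpoints carry parallel windows. What remains is that 7.1.6 does not repeat the window or deal with a first partial response after a component is dropped.
- **That serious events are also truncated, because section 8.2 runs "from the first dose of study drug through 30 days after administration of the last dose of ixazomib".** That passage governs reporting to the manufacturer. It does not define the data in the tables, and related serious events and new malignancies remain reportable afterwards.

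**Conclusion.** The point holds as a limitation of the tables that the protocol itself fixes. Against a count to 30 days after the last dose of any study drug, the tabulated percentages can only be equal or lower, and the cut-off is probably related to toxicity.

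The size cannot be determined from the protocol. Under the assumed hazards and the protocol's 4-cycle average, it is about 3 to 6 percentage points. A much larger shortfall needs longer treatment than the protocol expects on average. It could apply to patients who stay on treatment well beyond 4 cycles, whose further data go into the final report, but it should not be taken as the expected size at the primary analysis.

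The documents do not show that harm is under-reported relative to benefit. This is a worthwhile, inexpensive improvement and does not undermine the design.

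**What to change.** 1. In section 7.1.7, add a treatment-emergent adverse event table on the Safety Set from first dose to 30 days after the last dose of any study drug, the end point already used for the worst-grade listings. Present it beside the combination-only table, with the window stated in each title.
2. In section 7.1.6, repeat the response window of section 3.1 and state whether a first partial response reached after a component has been permanently dropped counts towards the response rate.

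The cost is a few lines of wording and one additional table from adverse event data already collected. The added percentages will probably look somewhat less favourable than the combination-only ones.
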